The results presented also highlight the critical importance of obtaining data from tumor and blood in order to separate between clonal expansions of T cells that are likely to be tumor specific versus those associated with immune-related toxicity. In fact, a large number of clones were found to be expanded in the blood between day 43 and 88, with brisk decrease after termination of Ipi administration (not shown), consistent with prior reports of a similar effect of anti-CTLA4 antibodies related to toxicity but not response [53].

### **Experimental methods**

Serial blood for immune monitoring studies will be collected at baseline, end of radiation therapy, at the time of the first three infusions of ipilimumab, at the time of the first three infusions of nivolumab, at response evaluation (day 70), and at 6 month follow up. Small aliquots of PBMC will be used ex vivo for preparation of DNA and RNA, and the remainder preserved frozen until evaluation by flow cytometry and/or by functional assays. Biopsies of the lesion to be irradiated will be obtained at baseline in all patients. Optional post-treatment biopsy will be performed at Day 22 in patients with an accessible, non-irradiated metastasis. We expect approximately 50% of the patients to comply with the second tissue acquisition. The choice of a non-irradiated lesion is motivated by safety concerns, after RT.

### **Sub-sites:**

Samples collected at sub sites will be shipped directly to the WCM via overnight shipping. We request that the sites notify the WCMC research team regarding number of patient samples being shipped and the tracking number of the specimens. Please refer to Appendix 1 for more information.

#### *a- Evaluation of systemic T cell populations and MDSC.*

In NCT02221739 we have observed a significant increase in Treg and in PD-1+ CD8 T cells in pts with PD but not in responders at day 22. In contrast a significant decline in MDSC was seen in responders (not shown). Additional trends were detected in other cell subsets including CD56bright and CD56dim NK cell subsets and in their expression of NKG2D. While hypothesis-generating these changes were not statistically significant, in part due to the small number of patients evaluated. To further evaluate the mechanistic and predictive value of the changes in immune cell subsets in peripheral blood during treatment with RT+Ipi and Ipi+Nivo, multi-color flow cytometry will be used to characterize T cells, NK cells and myeloid cells for the expression of multiple markers, including ICOS, CD27 (marker of activation and memory T cells), CD134 (marker of acutely activated T cells and involved in maintenance of response), CD137 (expressed mainly on CD8 T cells and involved in proliferative responses post-activation), CD154/CD40L (acutely activated CD4 T cells), CD152/CTLA-4, CD272/BTLA, CD279/PD-1 and TIM-3, which are expressed post-activation and associated with suppression/T cell exhaustion[54]. Additionally, T cells will be stained for the proliferation marker Ki67, and transcription factor EOMES, since changes in these markers have been reported to be associated with outcome and immune-related adverse events (irAE). CD8 T and NK cells will also be stained for NKG2D expression, a receptor implicated in their function and in response to anti-CTLA-4 (see below). Treg cells will be characterized for expression of surface markers (CD4, CD25, CD127, CD45RA) and transcription factors (FoxP3, Helios). Finally, MDSC (Lin- CD14+HLA-DRneg/low) will be evaluated to validate the significance of their decrease at day 22 as a potential predictor of response to treatment. Functional assays to test the suppressive activity or effector function of MDSC, NK, and T cell subsets will be performed if warranted.

*b- Evaluation of TCR repertoire changes in blood and tumor following treatment.*

TCRB repertoire analysis will be performed using genomic DNA (gDNA) from peripheral blood mononuclear cells (PBMC) and ImmunoSEQ hsTCRB (Deep) assay as described above. Genomic DNA (2 ug) will be prepared from paraffin tumor tissue and snap frozen PBMC. If <2ug are obtained, all available extracted DNA will be used. For each tumor sample, percentage of T cell infiltration in the tumor will be estimated using a droplet digital PCR technique. TCRB overlap between tumor and blood, and between each site before and after treatment, will be calculated for each patient as described [55]

*c- Evaluation of tumor mutational burden by whole-exome NGS and identification of potential neoantigens recognized by T cells.*

To investigate the mutational burden in NSCLC patients and identify tumor-specific mutations, whole exome NGS of tumor from pre-treatment (and post-treatment, if available) biopsy and normal tissue (blood) will be performed at the WCMC genomic core and data analyzed with the support of the bioinformatics core. To this end, DNA from each sample will be used to prepare barcoded libraries using Kapa Low-Throughput Library Preparation Kit Standard (Kapa Biosystems). The pooled capture library will be sequenced on an Illumina HiSeq 2500 sequencer using the 2x100 paired-end cycle protocol. Sequencing results will be demultiplexed and converted to FASTQ format using Illumina Bcl2FastQ software. The reads adapter and quality trimmed with Trimmomatic [<http://www.ncbi.nlm.nih.gov/pubmed/24695404>] will be aligned to the human genome using the Burrows-Wheeler Aligner [<http://www.ncbi.nlm.nih.gov/pubmed/19451168>]. PCR duplicates are marked using Picard toolkit [<http://www.ncbi.nlm.nih.gov/pubmed/23104886>]. Further local indel realignment and base-quality score recalibration will be performed using the Genome Analysis Toolkit (GATK) [<http://www.ncbi.nlm.nih.gov/pubmed/21478889>]. SNGs will be generated with MuTect [<http://www.ncbi.nlm.nih.gov/pubmed/23396013>] and indels with SomaticIndelDetector. ANNOVAR [<http://www.ncbi.nlm.nih.gov/pubmed/20601685>] will be used to annotate variants with functional consequence on genes as well as identifying presence in dbSNP. For each tumor we will obtain data on the number and type of single nucleotide variations (SNVs) and short insertions and deletions (Indels), and non-synonymous mutations. We will explore whether the number of total and non-synonymous mutations correlates with response to treatment.

In addition, in collaboration with [name] at NYU, we will explore the tumor neoantigen landscape. Non-synonymous mutation data will be filtered for gene expression using data obtained from RNA-Seq performed on the same tumor, and potential T cell epitopes analyzed using predictions for proteosomal processing and HLA class I and class II binding using NetChop Cterm3.0 and NetMHC3.2 algorithms.

**Objective 2.4:** To explore whether serum markers levels and their changes are associated with response.

#### **Rationale and preliminary data**

Our preclinical data show that RT-induced cancer cell intrinsic IFN $\beta$  production is critical for the priming of T cell responses capable of mediating an abscopal effect in combination with anti-CTLA-4 (Vanpouille-Box et al., manuscript in preparation). Importantly, a similar mechanism may be active in patients, since we detected a significant increase in IFNb at day 22 in serum of responders to RT+ipi (not shown). In addition, recent data have demonstrated the predictive nature of baseline levels of sMICA and CXCL11 for pts treated with ipi[56]. Interestingly, while high levels of sMICA were associated with poor survival in ipi-treated melanoma patients, in NYU NCT02221739 trial we have found a statistically significant increase in antibodies to sMICA

( $p=0.01$ ) and sMICB ( $p=0.0004$ ) at day 22 compared to baseline only in responding pts, suggesting that antibodies that block the soluble MICA molecules may restore recognition of the MICA/B+ tumor cells by NK and CD8 T cells[57]

### Experimental methods

Serial serum samples will be used to measure IFN $\square$  and CXCL11 by ELISA. sMICA, sMICB and antibodies anti-sMICA and anti-sMICB will be measured in serum by ELISA using recombinant MICA/B protein and anti-human MICA mAb, in collaboration with [name] (Dana Farber) with whom we have an ongoing collaboration. MICA expression in tumors will be tested by IHC. sMICA/B and anti-sMICA/B antibody levels, and expression levels of NKG2D in circulating CD8 and NK cells will be plotted over time to identify the nature of the changes and summarized using longitudinal mixed effects regression models that incorporate the repeated observations over time (fixed effects) within the same patient (random effect) and missing observations. Baseline levels and changes from baseline at the time of post treatment biopsy will be plotted for each of these markers and correlation coefficients with 95% confidence intervals will be estimated to evaluate the association between the serum and tumor marker levels.

### Objective 2.5: To explore associations of ORR with changes in the microbiome

While immune checkpoint blockade results in remarkably prolonged disease control in a subset of patients [58, 59] modulators of this phenotype are not well understood. Accumulating evidence suggests the gut microbiota play a critical role in response to both anti-PD-L1 efficacy and CTLA-4 blockade: two recently published studies by Vetizou *et al.* and Sivan *et al.* demonstrated in mouse models that the gut microbiome critically impacts response to immunotherapy [58, 59]. Remarkably, by altering the composition of commensal microbiota, the response to CTLA-4 blockade and anti-PD-L1 therapy could be manipulated and therapeutic response markedly enhanced. These pre-clinical studies provide strong rationale for our hypothesis that the human gut microbiome composition will correlate with response to ICB and RT. Identification of commensal organisms harbored in patients with heightened antitumor immune response can ultimately be manipulated to achieve desired outcomes in a greater proportion of patients. Fecal transplant is an established clinical technique whereby microbiota can be transferred into humans to induce select therapeutic outcomes, providing direct clinical applicability of any findings [30].

The study by Vetizou *et al.* underscores the dependence of CTLA-4 blockade on commensal microbiota [59]. First, the authors demonstrate that anti-CTLA-4 therapy is ineffective in mice that are housed in germ-free cages or treated with antibiotics.

By transferring specific gut microbiota back into antibiotic-treated or germ-free mice, the anticancer efficacy of CTLA-4 blockade could be recovered. The transfer of T cells specific to *Bacteroides fragilis*, or immunization with dendritic cells exposed to *B. fragilis* polysaccharides, also restored the antitumor effect of CTLA-4 blockade. Additionally, Vetizou *et al.* explored human gut microbiome changes in 25 malignant melanoma patients treated with CTLA-4 blockade, who at baseline fell into three microbial cluster patterns (Clusters A-C). During treatment, the microbial composition altered, becoming more similar to cluster pattern "C" and distant from cluster pattern "B". Subsequent fecal transplantation from cluster C patients into mice resulted in a significant response to CTLA-4 blockade, whereas transplantation from cluster B patients had no response, providing evidence that host gut microbial composition has a significant impact on likelihood of ICB success.

Sivan *et al.* likewise provides compelling data supporting the importance of gut microbiota in

determining treatment efficacy to ICB [58]. The authors compared growth of melanoma cell lines in two sets of mice harboring distinct gut microbiota, with differential tumor growth and response to PD-L1 therapy, and identified a specific bacterial species, *Bifidobacterium*, to be associated with antitumor immunity. By transferring *Bifidobacterium* from JAX mice to poorly-responding TAC mice, the authors were able to improve baseline anti-tumor immunity, and significantly enhance anti-PD-L1 therapy response. The therapeutic effect of *Bifidobacterium* was established to arise from altered dendritic cell function and increased priming of tumor-specific CD8+ T cells. Only live bacteria could achieve this effect, implying that augmentation of dendritic cell function requires direct interaction of host cells with gut microbiota [30]. These novel findings signify that the gut microbiome composition impacts response to anti-PD-L1 therapy and can be manipulated to enhance treatment response, providing impetus for similar analyses in human subjects.

Taken together, the above preclinical studies lend strong support towards collection of gut microbiome samples from patients enrolling on all future immunotherapy studies. We propose to collect stool samples from study patients before treatment and at day 21, 3 months and 6 months for analysis of microbiome composition and changes after ICB and RT. Both pre-clinical and clinical data demonstrate that the addition of RT to ICB creates a robust immune response, eliciting anti-tumor immune responses in otherwise non-responding patients. Given that we expect a similar heightened response in our proposed study, our patient cohort with its expected dichotomous outcomes will be particularly suitable for microbiome analysis. The results will be an important step towards understanding, and ultimately harnessing, the interplay between the human gut microbiome and anti-tumor immune response.

**Methods** Stool collection will occur before treatment, at day 22, day 70 and at 6 months follow up to explore changes of the microbiome during ICB. Bacterial diversity and taxonomy will be estimated by high throughput sequencing (HTS) of 16S rRNA amplicons, using the MiSeq platform in the Genomic Technology Core Lab. Methods have been established in the [name] Lab and proven to yield accurate and reproducible results.[60, 61] Analysis will be based on the QIIME (Quantitative Insights into Microbial Ecology) software package developed by the Knight lab, [62] and machine learning analyses developed by NYU Center for Health informatics and Bioinformatics (CHIBI) investigators working on NYU Human Microbiome Program studies [63, 64](64,65). Appendix 10 describes the protocol for stool collection.

#### **Sub-sites:**

Samples collected at sub sites will be shipped directly to the WCM via overnight shipping. We request that the sites notify the WCMC research team regarding number of patient samples being shipped and the tracking number of the specimens. Please refer to Appendix 10 for more information.

## **5.0 SUBJECT SELECTION CRITERIA**

For entry into the study, the following criteria **MUST** be met:

### **5.1 Inclusion Criteria**

- 1) Ability to understand and the willingness to sign a written informed consent document;
- 2) Histologic diagnosis of NSCLC;
- 3) Patients with an EGFR sensitizing mutation must have received an EGFR tyrosine kinase inhibitor (osimertinib, erlotinib, gefitinib or afatinib) and patients with ALK translocation must have received anti-ALK therapy.

- 4) Patients must have at least two distinct lesions, with one of at least 1 cm or larger in its largest diameter. Patients may have additional non-measurable metastatic lesions (e.g., bone metastases);
- 5) If the patient has received prior systemic therapy, an interval of 2 weeks from last therapy is required;
- 6) Patients must have recovered from the toxic effect(s) of the most recent anti-cancer treatment to NCI CTCAE Grade 1 or less (except alopecia).
- 7) Patients must have adequate organ and marrow function as defined by initial laboratory tests:
  - WBC  $\geq 2000/\mu\text{L}$
  - ANC  $\geq 1.5/\mu\text{L}$
  - Platelets  $\geq 100 \times 10^3/\mu\text{L}$
  - Hemoglobin  $\geq 9 \text{ g/dL}$
  - Creatinine  $\leq 1.5 \times \text{ULN}$
  - AST/ALT  $\leq 2.5 \times \text{ULN}$ , or  $\leq 5 \times \text{ULN}$  if liver metastases are present.
  - Bilirubin  $\leq 1.5 \times \text{ULN}$ , (except patients with Gilbert's Syndrome, who must have a total bilirubin  $\leq 3.0 \text{ mg/dL}$ ;
- 8) Performance status ECOG 0-1 or Karnofsky  $\geq 70\%$ ;
- 9) Men and women, ages  $> 18$  years of age;
- 10) Life expectancy  $> 3$  months;
- 11) Patients may have brain metastases if these are stable for at least 2 weeks (including radiosurgery treated lesions) and patients are not symptomatic or steroid dependent; Baseline MRI will be required." Note these lesions are not considered primary targets for the purposes of this protocol.
- 12) Patients in this study may not use vaccines for the treatment of cancer for up to one month before the first dose of ipilimumab. Concomitant systemic or local anti-cancer medications or treatments are prohibited while receiving study treatments.
- 13) Women of childbearing potential (WOCBP) must be using an adequate method of contraception to avoid pregnancy throughout the study and for up to 5 months after the study.  
WOCBP include any female who has experienced menarche and who has not undergone successful surgical sterilization (hysterectomy, bilateral tubal ligation or bilateral oophorectomy) or is not postmenopausal [defined as amenorrhea  $\geq 12$  consecutive months; or women on hormone replacement therapy (HRT) with documented serum follicle stimulating hormone (FSH) level  $> 35 \text{ mIU/mL}$ ]. Even women who are using oral, implanted or injectable contraceptive hormones or mechanical products such as an intrauterine device or barrier methods (diaphragm, condoms, spermicides) to prevent pregnancy or practicing abstinence or where partner is sterile (e.g., vasectomy), should be considered to be of child bearing potential. WOCBP must have a negative serum or urine pregnancy test (minimum sensitivity 25 IU/L or equivalent units of human chorionic gonadotropin (hCG)) within 72 hours prior to the start of study medication.
- 14) Men should use avoid impregnating women during study and for 7 months after the study.

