***“Innovative immune monitoring in a clinical trial of radiotherapy and immune checkpoint blockade”***

**PROTOCOL SYNOPSIS**

[figure not shown]
[figure not shown]
Protocol Title	Radiation and immune checkpoints blockade in metastatic NSCLC
Sites	Weill Cornell Medicine – New York Presbyterian Columbia University, New York Presbyterian

Study Schema	
Metastatic NSCLC patients with a minimum of two metastatic lesions (at least one measurable) are eligible if they have an ECOG Performance Status of 0-1. Patients must be willing to undergo a required pre-treatment biopsy prior to enrolling onto the study.
 
Non-ablative radiotherapy (6GyX5) is directed to one lesion on day 1 with ipilimumab 3 mg/kg (<math>\pm</math> 24hrs from first RT dose). On day 22 the combined treatment of ipilimumab plus nivolumab will start (nivolumab 360mg q 3 weeks, ipilimumab 1mg/kg q 6 weeks), and administered until evidence of progression. Patients are re-imaged at Week 9 (day 70 <math>\pm</math> 7) to evaluate for response (defined as an objective response by RECIST of the measurable metastatic sites outside the radiation field). This response will be evaluated assessing clinical and PET/CT responses in the non-irradiated measurable metastatic sites using RECIST 1.1.

Trial Objectives	
Primary Objectives:
 
To enhance the ORR to the combination of Ipi/Nivo in metastatic NSCLC by preceding it with a combination of Ipi/RT to convert the irradiated tumor into an in situ vaccine
 
Secondary objectives:
 
To explore whether early changes in TCR repertoire in peripheral blood are associated with response to treatment
 
To explore if serum markers levels/changes are associated with response
 
To explore associations of ORR with changes in the microbiome
 
Progression Free survival and Overall Survival (OS)
 
Time to progression and Duration of response (DOR)

Study Design	
A Simon's two-stage optimal design is chosen for this trial. Fifteen patients are required for stage 1. If 5 or more responses are seen, then the trial will proceed to stage 2 and an additional 29 patients will be enrolled and treated. If a total of <math>\geq</math> 18 objective responses are demonstrated the trial will achieve its main endpoint. We expect to accrue up to a total of 48 patients, independently from their PD-L1 status.

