#### 4.0 STUDY DESIGN

A Simon's two-stage optimal design is chosen for this trial, thus 15 patients are required for stage 1. If 5 or more responses are seen then the trial will proceed to stage 2 and an additional 29 patients will be enrolled and treated. If a total of  $\geq 18$  objective responses are demonstrated the trial will achieve its main endpoint.

We expect to accrue up to a total of 48 patients, independently from their PD-L1 status.

**Objective 2.1:** To demonstrate safety of combining initial concurrent radiotherapy and Ipilimumab as an induction regimen to the combination of Ipi/Nivo in NSCLC

A Simon's two stage design study of combined RT and Ipi (RT-Ipi), followed by maintenance of ipi/nivo is proposed for patients with metastatic NSCLC. Bristol-Myers Squibb (BMS) will provide drug and study support (ipilimumab and nivolumab) to patients on study (see letter of commitment from BMS).

Eligibility criteria: Patients  $>18$  years of age with histologically proven metastatic NSCLC, at least two measurable sites of disease, adequate organ and bone marrow function, ECOG PS 0-1 or Karnofsky  $\geq 70\%$  and informed consent for participation. Systemic or local anti-cancer therapies must be completed at least 2 weeks before the start of treatment. Baseline PET/CT or CT (chest, abdomen, and pelvis) is required within 4 weeks from accrual.

Treatment: At study entry all measurable metastatic lesions identified clinically or at PET/CT are recorded. Choice of the metastasis to be biopsied before and after RT-Ipi is based on ease of access (lymph nodes and subcutaneous metastases are preferred) and the estimated lowest risk for complications associated with tissue acquisition. The treatment starts a week after biopsy (during this week patients undergo CT simulation for radiation therapy). A regimen of 6 Gy X 5 daily fractions will be delivered to the biopsied lesion. Patients will receive ipi 3 mg/kg i.v. over 30 minutes initiated within 24 hours of the first dose of RT to the biopsied measurable lesion, conformally or by IMRT, with image guidance, to maximally spare normal tissue. At day 22 patients are started on the ICB combination of nivolumab 360 mg q 3 weeks, ipi 1mg/kg q 6 weeks, administered until evidence of progression. Patients will be re-imaged by CT between days  $70 \pm 7$  days (Week 9) and evaluated for response.

[figure not shown]

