## 5.2 Exclusion Criteria

1. Patients having no lesions outside the field of radiation thus nullifying the ability to measure

an abscopal effect;

2. Autoimmune disease: Patients with a history of inflammatory bowel disease are excluded from this study as are patients with a history of symptomatic auto immune disease (e.g., rheumatoid arthritis, progressive systemic sclerosis [scleroderma]), systemic lupus erythematosus, autoimmune vasculitis [e.g., Wegener's granulomatosis];
3. Patients with a history of symptomatic interstitial lung disease OR a history of (non-infectious) pneumonitis that required oral or IV steroids or current pneumonitis. Patients with resolved RT pneumonitis are eligible.
4. Patients with uncontrolled HIV infection. Note: participants with a plasma HIV viral load less than 200 copies/mL are eligible.
5. Patients with active Hepatitis B and Hepatitis C infection. Patients undergoing active therapy will be excluded from the trial.
6. Any underlying medical or psychiatric condition, which in the opinion of the Investigator, will make the administration of study drug hazardous or obscure the interpretation of adverse events (AEs), such as a condition associated with frequent diarrhea;
7. Concomitant therapy with any of the following: IL-2, interferon or other non-study immunotherapy regimens; cytotoxic chemotherapy; immunosuppressive agents; other investigation therapies; or chronic use of systemic corticosteroids; Tyrosine Kinase inhibitors such as Erlotinib;
8. Women and men who are unwilling or unable to use an acceptable method to avoid pregnancy for the entire study period and for at least 5mos (women) or 7mos(men) weeks after cessation of study drug, or have a positive pregnancy test at baseline, or are pregnant or breastfeeding;
9. Prisoners or subjects who are compulsorily detained (involuntarily incarcerated) for treatment of either a psychiatric or physical (e.g., infectious) illness.
10. Patients with mixed NSCLC/SCLC histology are excluded from this trial.

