## 8.0 RADIATION THERAPY GUIDELINES

### 8.1 Planning

After informed consent is obtained, a measurable lesion that is accessible for biopsy is selected by the treating physician as the site for local radiotherapy under Standard of Care practices to establish a diagnosis. The area of interest is imaged at CT planning for conformal treatment. There is no contrast media used in the CT planning. There is an exposure to small amounts of radiation with the use of CT scan. CT scan thickness should be  $\leq 0.5$  cm through the tumor bed region. These images will be used in 3D treatment planning in accordance with the dose specification constraints.

The CTV is defined as the lesion of interest with the expected motion changes, while the PTV is the CTV plus a margin  $\leq 1$  cm, dependent on the anatomical location, to account for setup uncertainty. While gating is not part of the current conformal setting at Stich Radiation Center, WCM, efforts are made to consistently treat chest and abdominal lesions with the patient maintaining shallow breathing, to limit the movement of the volume treated during respiration.

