### **8.4 On Study Evaluations**

As summarized in the Study Calendar, patients are evaluated pre-treatment for definition of metastatic sites with PET/CT or CT (CAP). At least two measurable metastatic sites are identified, and one of these lesions will be selected by the investigator for RT treatment with the goal of minimizing potential toxicity from RT. All lesions are followed per modified WHO criteria.

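### The lesion requirement is stated in two ways, and the looser one can admit a patient with no measurable lesion outside the radiation field

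*Combined protocol and SAP*

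**What the plan says.** **Looser version.** The synopsis (Study Schema) asks for "a minimum of two metastatic lesions (at least one measurable"). Section 5.1, criterion 4, opens: "Patients must have at least two distinct lesions, with one of at least 1 cm or larger in its largest diameter". It continues: "Patients may have additional non-measurable metastatic lesions (e.g., bone metastases").

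**Stricter version.** The eligibility paragraph in Section 4.0, under Objective 2.1, asks for "at least two measurable sites of disease". Section 8.4 says: "At least two measurable metastatic sites are identified, and one of these lesions will be selected by the investigator for RT treatment".

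**Radiotherapy target.** Section 8.1 states that "a measurable lesion that is accessible for biopsy is selected by the treating physician as the site for local radiotherapy". The synopsis, Section 4.0 and Section 14.0 all leave the irradiated lesion out of the response assessment. Sections 4.0 and 14.0 also leave it out of the baseline measurement.

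**Endpoint.** The synopsis has response "defined as an objective response by RECIST of the measurable metastatic sites outside the radiation field", and Section 4.0 agrees.

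**Exclusion 1 (Section 5.2)** removes "Patients having no lesions outside the field of radiation thus nullifying the ability to measure" an abscopal effect. It does not require the lesion outside the field to be measurable.

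**Evaluability.** Section 4.0, under Objective 2.2, calls a patient evaluable who had measurable disease at baseline and a scan at 9 weeks. It does not say where that disease must lie. It adds that patients replaced for being non-evaluable leave the denominator. The accrual-goal entry in the synopsis allows up to 4 extra patients, for withdrawals and for the non-evaluable.

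**The concern.** Out-of-field response is the primary endpoint, so every patient needs at least one measurable lesion that is not irradiated. Sections 4.0 and 8.4 secure this. The synopsis does not, and neither does the first sentence of criterion 4. Section 5 is the list that sites would naturally screen from, and two sites enrol.

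If a patient without such a lesion enters, two questions arise: whether a response could ever be recorded, and whether the patient belongs to the 44 on whom the decision rule is applied.

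**Working it through.** **Step 1: follow one patient through the text.** Take one measurable lung lesion and one bone metastasis. Section 13.4 classes bone lesions as non-measurable.

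| Provision | Result |
|---|---|
| Synopsis: two lesions, one measurable | passes |
| Criterion 4, first sentence | passes |
| Exclusion 1: some lesion outside the field | not excluded |
| Section 4.0: two measurable sites | fails |
| Section 8.4: two measurable sites, one irradiated | fails |

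Under Section 8.1 the lung lesion is the one irradiated. No target lesion is then left. In the Section 13.5 table every row leading to CR, PR or SD starts from a target-lesion status, so this patient can be scored as progressing but has no defined way to respond.

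There is also a smaller gap. Criterion 4 uses the largest diameter, whereas Section 13.4 requires a node to reach 15 mm in short axis. A node can meet the 1 cm figure and not be measurable.

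**Step 2: reproduce the plan's design.** The inputs come from the synopsis and Section 17: null rate 31%, alternative 51%, stop if 4 or fewer of 15 respond, 44 in total, success at 18 or more.

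P(success) = Σ over x = 5 to 15 of Bin(x; 15, p) × P(Bin(29, p) ≥ 18 − x)

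- At p = 0.31: 0.0946 (stated 0.10).
- At p = 0.51: 0.9000 (stated 90%).

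The design is reproduced with 18. Section 17.2 prints 17, which would give 0.150 and 0.925. That is a separate discrepancy, and 18 is used below.

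**Step 3: literal reading of evaluability.** The patient counts among the 44 and cannot respond. The documents do not say how many such patients there would be, so k is an assumption. Let J be the number of the k patients who fall in stage 1, hypergeometric with (44, k, 15):

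P(success) = Σ over j of P(J = j) × Σ over x = 5 to 15 − j of Bin(x; 15 − j, p) × P(Bin(29 − k + j, p) ≥ 18 − x)

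| k of 44 (assumed) | Power, others at 51% | Stage 1 stop, others at 51% | Type I error, others at 31% |
|---|---|---|---|
| 0 | 0.900 | 0.051 | 0.095 |
| 1 | 0.876 | 0.060 | 0.077 |
| 2 | 0.848 | 0.071 | 0.062 |
| 4 | 0.776 | 0.097 | 0.039 |

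Multiplying the response rate by 1 − k/44 instead of fixing the count gives power of 0.874, 0.843 and 0.766. The conclusion is the same.

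**Step 4: contextual reading.** The irradiated lesion is not part of the baseline measurement, so the patient has no measurable disease at baseline. The patient is non-evaluable, is replaced and leaves the denominator. Up to 4 non-evaluable patients in total (48 − 44), 44 evaluable patients remain and power stays at 0.900. With 5 or 6 among 48, 43 or 42 remain. Power is then 0.883 or 0.862 if the threshold of 18 is kept, which is a further assumption because the plan gives no rule for fewer than 44.

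**The case against.** Section 5 does not stand alone. The Section 4.0 paragraph is labelled as eligibility criteria, and Section 8.4 repeats its rule as a pre-treatment step, so the patient would have to fail two passages and still be enrolled. Criterion 4's remark on additional non-measurable lesions can be read to mean that the two required lesions are measurable, and exclusion 1 states that its purpose is measurement. All of this stands, and it makes such an enrolment less likely. It does not remove the conflict: the synopsis expressly needs only one measurable lesion, however criterion 4 is read.

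On evaluability, the contextual reading is the more natural one, because the same section first takes the irradiated lesion out of the baseline measurement. What remains is a missing location in the definition.

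A reader might infer three stronger points, none of which the documents support:

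- *The synopsis and Section 4.0 disagree on who may be replaced.* One sentence in Section 4.0 names only withdrawals and missed 9-week evaluations. A later sentence there treats non-evaluability as a ground for replacement, and the synopsis and Section 17.2 do the same.
- *The false-positive rate is inflated.* Counting patients who cannot respond lowers it.
- *Such patients have been enrolled, or power has been lost.* No count is given, and the losses in Step 3 apply only to the literal reading.

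**Conclusion.** The contradiction is in current text and bears on the primary endpoint. The synopsis and the first sentence of criterion 4 are looser than Sections 4.0 and 8.4, and the gap can admit a patient with no defined route to a response. The evaluability definition does not state that the measurable disease must lie outside the field, so the two readings give different denominators.

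The size is conditional. Under the literal reading, 1, 2 or 4 such patients would cost about 2, 5 or 12 percentage points of power (0.900 to 0.876, 0.848 or 0.776), and type I error would fall. Under the contextual reading there is no loss until non-evaluable patients of every kind exceed 4. The number of such patients is assumed throughout. The wording should be corrected. The point gives no ground for doubting the design's stated error rates.

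**What to change.** 1. Bring the synopsis, criterion 4, exclusion 1, Section 4.0 and Section 8.4 to one requirement that guarantees at least one lesion outside the planned field that is measurable under Section 13.4, including the 15 mm short axis for nodes. The existing rule in Sections 4.0 and 8.4 does this if it is worded as two measurable lesions, one irradiated and one outside the field. Scoring itself needs only the second, so the sponsor should state whether the irradiated lesion must also be measurable, as Sections 8.1 and 8.4 now say.
2. Reword exclusion 1 to exclude patients with no *measurable* lesion outside the field.
3. In Section 4.0, define evaluable as having measurable, non-irradiated disease at baseline and a 9-week imaging evaluation.
4. For patients already enrolled, decide this from baseline imaging only, without reference to response. Report the ORR with and without anyone reclassified. The trial is single-arm with known treatment, so a later change of evaluability could otherwise remove known non-responders from the denominator.

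The cost is amendment wording and a review of baseline records. Eligibility becomes slightly narrower than the synopsis and the looser reading of criterion 4. No new procedure is needed, because baseline imaging already records these lesions.
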